EQ5D5L-VAS	EuroQol 5D 5L Visual Analogue Scale
FQ	Fear Questionnaire
GAD	Generalized Anxiety Disorder
GAD-7	7-item Generalized Anxiety Disorder Questionnaire
GCP	Good Clinical Practice
ICF	Informed Consent Form
ICH	International Conference on Harmonisation
mRS	Modified Rankin Scale
PI	Principal Investigator
PIS	Participant Information Sheet
QA	Quality Assurance
RCT	Randomized Controlled Trial
REC	Research Ethics Committee
SAE	Serious Adverse Event
SAR	Serious Adverse Reaction
SOP	Standard Operating Procedure
SUSAR	Suspected Unexpected Serious Adverse Reaction
TIA	Transient Ischaemic attack

1 INTRODUCTION

1.1 BACKGROUND

Anxiety affects around a quarter of stroke patients and can be disabling. A Cochrane review in 2017 concluded that the three randomized controlled trials (RCT) of anxiety intervention in stroke carried high risk of bias and were of small sample size, thus provided insufficient evidence to guide treatment.

[figure not shown]
We carried out an observational study using psychiatric interviews to determine the commonest anxiety subtypes and anxiety-provoking situations to inform the targets of a psychological intervention. Based on these findings we developed a complex intervention consisting of cognitive behavioural therapy (CBT) techniques specifically adapted to the anxiety issues reported by patients following a stroke or transient ischaemic attack: the TASK-CBT intervention.

Scientific basis for TASK-CBT

Phobic disorder was the predominant anxiety subtype after stroke (Figure 1) in our prospective cohort (n=175), consistent with three earlier studies that conducted psychiatric diagnostic interviews (1). Phobic anxiety is characterized by fear disproportionate to defined situation(s) and marked avoidance. Generalized anxiety disorder (GAD) is persistent & unremitting anxiety about multiple daily events. In non-stroke populations, exposure therapy is effective at treating phobic disorders in RCTs(2), while GAD responds to selective serotonin reuptake inhibitors, short-term benzodiazepines, and/or other cognitive behavioural techniques e.g. cognitive restructuring, problem solving(3, 4). Anxiety disorder at 3 months post-stroke was associated with poorer functional independence and quality of life even in a mild stroke & TIA sample(5).

[figure not shown]
We hypothesize that an intervention that does not target phobic anxiety after stroke is not effective at alleviating anxiety symptoms and will not improve functional independence and quality of life after stroke.

Figure 1. Frequency of phobic disorder and GAD at 3 months after stroke (n=175) (5)

To include exposure therapy in CBT there must be defined feared situation(s)/ stimuli. We quantified in our observational study, for the first time, the common anxiety-provoking situations/stimuli and maladaptive cognitive patterns affecting stroke survivors (Figure 2), and their associated avoidant behaviour. These findings informed targets for cognitive restructuring and exposure techniques used in the TASK-CBT intervention.

Figure 2. Common anxiety-provoking situations/stimuli in 38/175 with anxiety disorder)(5)

The TASK-CBT intervention and TASK-Relax (active comparator)

TASK-CBT intervention: Telephone-guided web-based CBT

There are two key modes of delivery within the TASK-CBT intervention:

- 1) **A course of 6 weekly telephone-guided sessions** (30-40minutes each) delivered over 6-12 weeks using the 'TASK therapist's manual & record'. Therapist (any stroke health professional—stroke nurse, rehab therapist, stroke doctor) receives training by [name]. Therapist meets with [name] and reviews record. All telephone-guided sessions are audio-recorded and transcribed to aid validation of the therapist's record.
- 2) **TASK-CBT treatment website** displays information, graphics, treatment videos, and online tasks covering all components of TASK-CBT

For participant's experience, please visit xxxxxxxxxxxxxxxx.
Temporary login: xxxxxxxxxxxxxxxx password: xxxxxxxxxxxxxxxx

The active comparator intervention: TASK-Relax website

- TASK-Relax is an online self-guided course of relaxation techniques.
- One telephone session (20 minute) at the start to guide participant how to use the TASK-Relax website
- The course is structured with 5 online tasks. An introductory video (with subtitles) provides simple instructions on how to use the TASK-Relax website throughout the trial period.
- The tasks contain videos of breathing exercise, muscle relaxation, relaxing imagery and sound clips to teach participants various relaxation techniques
- Participants are encouraged to take at least 5 minutes to practice a relaxation task daily in the long-term

For participant's experience, please visit xxxxxxxxxxxxxxxx
Temporary login: xxxxxxxxxxxxxxxx password: xxxxxxxxxxxxxxxx

Additional features common to both TASK-CBT and TASK-Relax intervention

- **Ongoing ‘anytime’ access** to the allocated website up to the end of the TASK trial period
- **Useful links** to external stroke resources—Chest Heart Stroke Scotland and Stroke Association websites
- **Regular text reminders** to improve intervention adherence & completion of data collection in the TASK trial. The text reminders continue throughout the trial period until data completion at primary endpoint
- Every participant is informed they will receive access to the website given to the other group
- Every participant receives a **TASK participant card as follow:**

A clinical trial of web-based treatments for anxiety after stroke
Participant card

Your first allocated treatment website: www.tasktreatment2.org

Your login:

Your password:

Please do not pass on your login details to other people

TASK CBT participant card front

Contact us if you require assistance

TASK [contact]

Email: [contact]

Date	Day	Time		
Sessions				
1	_____	_____	TASK 1	
2	_____	_____	TASK 2	
3	_____	_____	TASK 3	
4	_____	_____	TASK 4	
5	_____	_____	TASK 5	
6	_____	_____	TASK 6	
Study Survey 1	_____	_____		
Study Survey 2	_____	_____		
Feedback Survey	_____	_____		

Continue to use the website to help you manage your anxiety

Handy tips

- Monitor your anxious feelings, thoughts and
- Challenge unhelpful thoughts
 - Have a conversation with yourself
 - Be kind to yourself
- Frightened of a specific situation?
 - Face your fear in small gradual steps
 - Stay until the anxiety level starts to decrease

You will receive a link to the treatment given to the other group on completion of Study Survey 2

TASK CBT participant card back

A clinical trial of web-based treatments for anxiety after stroke Participant card

Your first allocated treatment website: www.tasktreatment3.org

Your login:

Your password:

TASK-Relax
participant card front

Please do not pass on your login details to other people

Do not hesitate to contact us if you require assistance

TASK [contact]

Email: [contact]

	Date	Day	Time	
Sessions				
1	_____	_____	_____	TASK 1 
2	_____	_____	_____	TASK 2 
3	_____	_____	_____	TASK 3 
4	_____	_____	_____	TASK 4 
5	_____	_____	_____	TASK 5 
6	_____	_____	_____	TASK 6 
Study Survey 1	_____	_____	_____	
Study Survey 2	_____	_____	_____	
Feedback Survey	_____	_____	_____	

Continue to use the website to help you manage your anxiety

Handy tips

Monitor your anxious feelings, thoughts and

Challenge unhelpful thoughts

Have a conversation with yourself

Be kind to yourself

Frightened of a specific situation?

Face your fear in small gradual steps

Stay until the anxiety level starts to decrease

You will receive a link to the treatment given to the other group on completion of Study Survey 2

TASK-Relax
participant card back

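### The TASK-Relax participant card repeats the TASK-CBT card's cognitive and graded-exposure tips and names no relaxation technique, so it does not match the comparator described in section 1.1

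*Combined protocol and SAP*

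**What the plan says.** Section 1.1 (Background) keeps the techniques of the two arms apart. On the observational work behind the trial it says: "These findings informed targets for cognitive restructuring and exposure techniques used in the TASK-CBT intervention". Of the comparator it says: "TASK-Relax is an online self-guided course of relaxation techniques". It then lists the comparator's content: "The tasks contain videos of breathing exercise, muscle relaxation, relaxing imagery and sound clips to teach participants various relaxation techniques". No cognitive or exposure element appears in that description. TASK-Relax has one 20-minute telephone session at the start and five online tasks, against six weekly guided telephone sessions for TASK-CBT.

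The same section then lists features shared by both arms. One of them is a participant card, and both cards are printed there. The second card opens with "Your first allocated treatment website: www.tasktreatment3.org" and closes with the TASK-Relax label and the words "participant card back". Its tips include "Challenge unhelpful thoughts", "Face your fear in small gradual steps" and "Stay until the anxiety level starts to decrease". It also prints session rows 1 to 6 and boxes for TASK 1 to TASK 6.

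Under section 5.2 the researcher posts each participant the card for the arm to which they were allocated. Section 8.2 plans descriptive clinical outcomes at T0, T1 and T2 and between-group differences, with no test named. Section 8.1 states that no sample size was calculated, because this is a feasibility trial.

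**The concern.** Cognitive challenge and graded exposure are the techniques that section 1.1 attributes to the intervention under test. Exposure is also central to the trial's rationale, because section 1.1 hypothesizes that a treatment that leaves phobic anxiety untargeted will not work. A card that tells comparator participants to face feared situations in steps gives them a short form of that technique.

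If the card is used as printed, the comparison in section 8.2 is between TASK-CBT and relaxation plus brief written cognitive and exposure advice. That is not the comparator described. If the advice has any effect, the likely direction is to bring the arms closer together.

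The trial's own data would not show the overlap. The fidelity measures in section 2.2.1 are the therapist record, the session transcripts, website analytics and online task completion, and none of them covers what the card says.

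**Working it through.** No formula applies to the main point, and the plan gives no figure to reproduce. The check sets the two cards and the section 1.1 description side by side.

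| Item | TASK-CBT card | TASK-Relax card | TASK-Relax as described in 1.1 |
|---|---|---|---|
| Website | tasktreatment2.org | tasktreatment3.org | Relaxation website |
| Tip lines | 7 | 7 | Not described |
| Cognitive or exposure technique | 3 lines | the same 3 lines | None listed |
| Named relaxation technique | 0 lines | 0 lines | Breathing, muscle relaxation, imagery, sound clips |
| Session rows | 6 | 6 | 1 telephone session |
| Task boxes | 6 | 6 | 5 online tasks |

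1. **Tips.** Six of the seven lines are complete and identical on both cards. The seventh, on monitoring feelings and thoughts, breaks off at the same point on both, so its ending cannot be compared. The three technique lines are the ones quoted above: one cognitive, two graded exposure. This sorting is a judgement, and the monitoring line could be counted as a fourth. The count of zero for relaxation rests on the readable text.

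2. **Is this a reading error?** Probably not. The second card has its own web address, its own front and back labels and differently worded contact text. It is separate text and not the first card read twice.

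3. **Was a template reused?** The session rows are the clearest sign. Six telephone sessions belong to TASK-CBT in section 1.1, and TASK-Relax has one. The task boxes are weaker evidence, because the task count varies for TASK-CBT too: section 2.2.1 lists tasks 1 to 6, while sections 6.1 and 7 give five.

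4. **Scale of possible exposure.**
   - Participants: the documents give a target of 40 and no allocation ratio. Assuming 1:1, 40 / 2 = 20 would hold the TASK-Relax card. Over ratios from 2:1 to 1:2 the figure runs from 40 / 3 ≈ 13 to 2 × 40 / 3 ≈ 27.
   - Time: T2 falls 20 to 30 weeks after randomization, so the card could be held for 20 × 7 = 140 to 30 × 7 = 210 days, less postal time.
   - Intensity: three unguided lines, against 6 × 30 = 180 to 6 × 40 = 240 minutes of guided TASK-CBT sessions.

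These figures bound who could hold the card and for how long. They do not estimate an effect on any outcome.

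**The case against.** The strongest reply is that nothing is hidden. Section 1.1 prints both cards under the features common to the two arms, so the tips may be a deliberate shared element. Calling TASK-Relax a relaxation course does not say that its participants receive nothing else. Part of this stands: intent cannot be settled from the documents. But the shared feature that section 1.1 names is the card, and no sentence says that cognitive or exposure advice is meant for both arms. The mismatched session rows fit a copied layout better than a planned common component.

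A second reply is that this is a clerical slip in an illustration, in a trial whose primary objectives are feasibility and harm. The limit on consequences stands. However, the card is posted to participants, so following the plan as printed changes what the comparator arm receives.

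A reader might also infer more than the documents support:

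- **That masking is broken.** Section 3 keeps participants unaware of the other group's type of treatment. The TASK-Relax card does not attribute its tips to the other arm, so a breach does not follow.
- **That the choice of active comparator fails.** The remark in section 1.2 on comparators and effect size concerns the type of control, such as usual care or waitlist. TASK-Relax remains an active comparator whatever tips the card carries.
- **That the harm data under objective 3 are compromised.** A change in reported unwanted effects from a few unguided lines is speculation, and the survey would still describe the intervention as delivered.
- **That tips have no place on the card.** Section 7 mentions the card as a record of completed surveys and tasks, in a list on complete data collection. That is one use of the card and not necessarily its only purpose.

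**Conclusion.** The point holds as a mismatch between the comparator's description and its participant material. The duplication of the tips is clear from the text. Contamination of the comparator arm is conditional on the cards being issued as printed, which the documents do not show. If they are, TASK-Relax participants hold brief cognitive and exposure advice before T2, and the descriptive between-group differences in section 8.2 carry slight contamination.

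The effect is probably small, and its size cannot be estimated from the documents. No powered comparison is affected, because none is planned. The figure of about 20 participants rests on an assumed 1:1 allocation. The point is worth correcting because the advice comes from the intervention under test and is easily removed.

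**What to change.** Reconcile the TASK-Relax card with section 1.1. Replace its tips with ones drawn from the TASK-Relax content, and make its session and task rows agree with the number of sessions and tasks described there. If cards with the printed text have already been issued, note this when the between-group differences are reported.

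The cost is one minor amendment and the reprint of one card. Sample size and timelines are unaffected.

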1.2 RATIONALE FOR STUDY

Research question

Is it feasible to compare the effectiveness of the telephone-guided web-based TASK-CBT with web-based self-guided TASK-Relax in a web-enabled randomized controlled trial?

Why is this study important to patients, health service and current policies?

Anxiety problems after stroke are common and disabling. There is little research evidence to guide how to treat anxiety after stroke. Access to psychological care after stroke is difficult. We need to deliver an anxiety intervention to large number of stroke and TIA patients, efficiently and economically to ensure its long-term sustainability in the NHS. Our intervention is developed in line with the Scottish Mental Health Strategy for 2017-2027.

Treatment to be tested

We know that cognitive behavioural therapy (CBT) works for anxiety in people who have not had a stroke. Many anxiety issues reported by stroke patients can potentially be targeted by CBT. We developed CBT treatment that are specifically tailored to stroke survivors. Before we can provide TASK-CBT to a large population of stroke survivors, we need to test whether these treatments have any real benefits to patients in a clinical trial setting.

Feasibility of our method to minimize bias in a RCT of psychological intervention

The type of comparator group in an RCT of psychological intervention can influence effect size(6). Rather than using a 'treatment as usual' (TAU) or waitlist control as comparator, we are comparing group receiving TASK-CBT & group receiving TASK-Relax (active comparator).

Establishing any harms of our intervention

It is not clear, but important to establish whether there is any potential harm of a telephone-guided web-based CBT intervention for stroke and TIA patients. We will do that by asking participants to complete a feedback survey at the end of the study period.

Feasibility in conducting a nationwide web-enabled RCT conducted by a single centre

We designed the trial procedures with the view of conducting a large-scale clinical trial that will recruit nationwide from a single centre in the future. We will use the feasibility data from this present study to refine our trial design.

Feasibility of measuring objective outcomes using a wrist-worn wearable device (a substudy)

Wearable device can collect objective physiological and behavioural measures, complementing and potentially replacing self-reported outcomes used in clinical trials of a wide range of interventions in

stroke and TIA patients. In a substudy we will assess the feasibility and acceptability of the GENEActive Original device in a clinical trial setting of stroke and TIA patients with anxiety.

2 STUDY OBJECTIVES

2.1 OBJECTIVES

2.1.1 Primary Objectives

Objective 1: Feasibility of web-enabled RCT procedures

Objective 2: Feasibility of TASK-CBT & TASK-Relax interventions

Objective 3: To establish any harm arising from TASK-CBT or TASK-Relax interventions

2.1.2 Secondary/ substudy objectives

Objective 4: Feasibility of wearing wrist-worn device (GENEActiv) for up to 210 days

3 STUDY DESIGN

- A parallel randomized controlled trial comparing TASK-CBT and TASK-Relax

Study schematic

- Method of masking/ blinding of participants to intervention allocation:
 - Participants are informed they will receive all TASK treatments designed for this trial by the end of the study period
 - Both interventions are referred to as TASK treatments in Participant Information Sheet (PIS) (The PIS electronic and paper versions) simply states that we are testing different treatments: ways to overcome anxiety, relaxation techniques, useful videos, weekly tasks, regular text reminders
 - Participants are not aware of what type of treatment is given to the other group until they get access to it after the primary endpoint
- The purpose of this design is to reassure participants that they are getting an active intervention
- **Substudy of the wrist-worn device GENEActiv Original**
 - The GENEActive Original device is a CE-marked wrist worn device used for in many research studies. <https://www.activinsights.com/actigraphy/geneactiv-original/>
 - The device measures light, temperature and acceleration data
 - Participants in this substudy are asked to try to wear this watch as continuously as possible for up to 60 days

- Simple instructions will be given to wear it on the non-paretic hand; avoid covering the light sensor; remove for shower/ bath and put it back on afterwards; remove if any skin irritation occurs and inform the TASK research team

4 STUDY POPULATION

4.1 NUMBER OF PARTICIPANTS

- We aim to recruit 40 participants into this feasibility RCT from NHS Lothian, 20 of whom for the substudy of the wrist-worn device

4.2 INCLUSION CRITERIA

1. Diagnosis of stroke (ischaemic, haemorrhagic), probable or definite transient ischaemic attack (TIA) & ocular TIA
 - For clinic patients diagnosis has to be at least one month ago
 - For ward patients, at least one month after discharge to community
2. Age 18 or over
3. Has access to internet and telephone
4. Has anxiety symptoms (at least one positive response to the 6 anxiety questions on the 'Sign up form') and would like to receive treatment
5. Has capacity to give informed consent
6. Able to talk on the telephone (assessed by research team + verbal fluency test on telephone)
7. Living within Lothian (all EH postcodes and FK1)

4.3 EXCLUSION CRITERIA

- Non-English speaking
- Already taking part in a clinical trial of treatment (drug or non-drug) intended to improve psychosocial outcomes e.g. stress, anxiety, depression, emotionalism, fatigue, social functioning, quality of life (as taking part in our study would affect the results in another trial)

*Being on a mood altering medication is not an exclusion criterion in TASK. We record whether participant is on a mood-altering medication during our data collection.

4.4 CO-ENROLMENT

- Participants cannot be co-enrolled to other clinical trials of treatment (drug or non-drug) intended to improve psychosocial outcomes e.g. stress, anxiety, depression, emotionalism, fatigue, social functioning, quality of life as co-enrolment is likely to influence outcomes in these trials
 - Our study sign-up form includes a routine question on whether the potential participant has already enrolled onto another research study. This is verified by the TASK research team
- Co-enrolment in an observational study, including one measuring psychosocial outcomes is permitted, but we will ask participant to first consider the potential burden of taking part in more than one research study.
 - Burden of co-enrolment in another observational study on psychosocial outcomes
 - Similar questionnaires
 - Follow ups may coincide with telephone sessions within TASK-CBT intervention
- Once enrolled onto the TASK trial we will make an entry onto TRAK record

5 PARTICIPANT SELECTION AND ENROLMENT

[figure not shown]
5.1 IDENTIFYING PARTICIPANTS

There are two methods of identifying potential participants. All methods encourage potential participants to visit the TASK recruitment website www.task4stroke.org where potential participants can begin the online sign up process themselves.

Recruitment method

Prospective recruitment

Discharge from ward or TIA clinic

For participant's experience, please visit www.task4stroke.org

i) *Prospective recruitment:*

Participants who are identified as having anxiety symptoms by clinical staff or at 1-month telephone screening* are encouraged to visit www.task4stroke.org

*part of clinical care, as recommended by the latest Royal College of Physician's Guideline Fifth Edition 2016 (2.12.1).

ii) *Retrospectively:*

[figure not shown]
TASK researchers [name], [name], [name], and [name] are also part of the direct care team for stroke and TIA patients at the Royal Infirmary of Edinburgh. They will identify potentially eligible participants from the Scottish Stroke Care Audit

database and SHARE (www.registerforshare.org) and check eligibility on hospital electronic health system (TRAK).

Letters of invitation and a 'TASK business card' will be sent to the potential participants on behalf of their treating physician. The letter advises patients to either seek GP advice or consider taking part in a clinical trial by visiting www.task4stroke.org if they are experiencing anxiety issues

We will publicise the TASK recruitment website www.task4stroke.org by disseminating TASK 'business card', PIS widely across the stroke services as above, on social media and via stroke charities.

TASK study recruitment website 'business' card

Any interested potential participant can either

- i. sign up themselves using the 'Sign up form' on www.task4stroke.org
- ii. contact the TASK research team by phone/ email for assistance in completing the online 'Sign up form' or request its paper version

